## 2.0 Background

### 2.1 Scientific Background and Gaps

Overweight and obesity are America's number one health concern. The prevalence of obesity in the US is greater than 36%, which is far above the Healthy People 2020 objective of less than 30.5%. Perhaps most concerning is the rate that obesity has increased, having doubled since 1970. As the second most preventable cause of death, obesity is a risk factor for diabetes, cardiovascular disease, stroke, and cancer, all major causes of death in the US. Addressing obesity through lifestyle interventions decreases the risk of developing type 2 diabetes, a disease which affects over 29 million people (9.3% of the US population). Diabetes is associated with serious complications, including cardiovascular disease, blindness, renal failure and lower extremity amputation. Although complications are preventable with proper medical and lifestyle management, including weight loss, nearly half of patients with diabetes do not have adequate glycemic control.

Primary care clinics may be an ideal setting for weight control interventions. Greater than 80% of Americans see a PCP regularly and access to primary care is expected to increase with health care reform. Further, as PCPs identify and treat the multitude of conditions affected by being overweight, including diabetes, they are ideally positioned to best engage their patients in weight management. The Centers for Medicare and Medicaid Services (CMS) implemented a healthcare procedure coding system code for intensive behavioral therapy (IBT) for obesity within primary care settings in 2012 to facilitate payment for addressing obesity, which was followed by universal coverage by insurers for IBT for adults of all ages in 2013. However, the impact of this coverage on patient-centered outcomes is largely unknown.

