To evaluate the impact of policy changes on these outcomes, we will examine how these outcomes change over time, in response to the policy changes. As descriptive analyses, we will plot the mean trajectory of each yearly outcome at clinic level, health system level and state level. The statistical modeling of patterns of changes in individual level outcomes will be carried out through multi-level mixed-effects models. The mixed-effects model is a common and popular modeling technique for longitudinal data. A mixed-effects model can accommodate within- and between-subjects variability, as well as serial correlations. In addition, it has the flexibility to incorporate time-dependent covariates, incomplete data, and heteroscedasticity of the variances and correlations. The mixed-effects model will be specified in a multi-level fashion so that different levels of variability (e.g., individual characteristics, social environment, built environment) can be taken into account. The pattern of changes in the outcome will be assessed for pre- and post-periods, respectively, based on the piecewise/segmented regression models. The slope of each segment indicates the trend of change in diabetes outcome in that period. Therefore, the change in the trend/slope post-policy implementation may reveal the actual impact of the new policy controlling for baseline level and trend. Such modeling strategies share the same spirit of interrupted time series analysis. While the classical interrupted time series design often generates a single long series of data, we have a large number of short series from each individual subject, namely, longitudinal data. Depending on the types of the outcomes, we will specify mixed-effects models based on logistic

regression for a binary outcome, Poisson regression for a count outcome and linear regression for a continuous outcome as detailed below.

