In the multi-level modeling, the first-level unit is the yearly measurement for the individual subject (pre- and post-policy), the second-level unit is the individual subject, the third-level unit is the health system or clinic within the health system (cluster), and the fourth-level unit is the state. We set year 2014 as time origin for Utah when considering the policy impact of the ACA. Let  $Y_{ijkt}$  denote the binary response of having controlled diabetes at year  $t$  since policy changes for the  $k^{\text{th}}$  subject within the  $j^{\text{th}}$  cluster of the  $i^{\text{th}}$  state,  $t = -5, -4, \dots, 0, 1, \dots, 5$ ,  $i = 1, 2, 3$ ;  $j = 1, 2, \dots, c_i$ , and  $k = 1, 2, \dots, n_{ij}$ , where  $c_i$  is the number of clusters within the  $i^{\text{th}}$  state and  $n_{ij}$  is the sample size within the  $j^{\text{th}}$  cluster of the  $i^{\text{th}}$  state. An individual subject may not be in the system for all 11 timepoints of measurement, so  $t$  will have a smaller range of values for that individual subject. Also due to the different timeline of policy changes, the number of years before and after policy changes may vary. The probability of having controlled diabetes,  $\mu_{ijkt} = E(Y_{ijkt}) = \Pr[Y_{ijkt} = 1]$ , can be described by the following segmented logistic regression model

$$\begin{aligned} \text{logit } \mu_{ijkt} &= \log \{\Pr[Y_{ijkt} = 1] / \Pr[Y_{ijkt} = 0]\} \\ &= \beta_{0ijk} + (t + 5) \beta_{1ijk} && \text{if } -5 \leq t \leq 0, \text{ pre-period before policy changes} \\ &= \beta_{0ijk} + 5 \beta_{1ijk} + t \beta_{2ijk} && \text{if } 0 \leq t \leq 5, \text{ post-period after policy changes} \end{aligned}$$

where  $\beta_{mijk}$  ( $m = 0, 1, 2$ ) are subject-specific regression parameters, with  $\beta_{0ijk}$  being the log odds of having controlled diabetes at  $t = -5$ , and  $\beta_{1ijk}$  and  $\beta_{2ijk}$  being the slopes (annual change in log odds) for the pre- and post-periods, respectively. In the framework of a mixed-effects model, each  $\beta_{mijk}$  is modeled by

$$\beta_{mijk} = \mathbf{x}_{mijk}^T \boldsymbol{\beta}_m + \mathbf{z}_{ij}^T \boldsymbol{\gamma}_{1ij} + \boldsymbol{\gamma}_{2mijk}$$

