## Subgroup analyses

Due to the heterogeneity of the population and a dynamic cohort in our study, we will investigate subgroup analyses to assess how the policy impact varies across different subgroups. Following the general modeling approaches as described above, we will examine the benefits of policy changes for different subgroups including (1) patients with insurance throughout the study period, (2) patients who obtained insurance after the policy changes, (3) patients without insurance throughout the study period, (4) patients newly enrolled in the system after policy changes, and (5) other subgroups of interest according to gender, age (e.g., age 65 and older), race-ethnicity. Meta-analysis has been a powerful approach to combining the effects of interest across different studies, different populations, and different subgroups. We will adopt this method to evaluate the average impact of policy changes across subgroups. A forest plot will be generated to reveal how the addition of a subgroup to the meta-analysis may affect the average policy impact.

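### The planned meta-analysis across subgroups draws on overlapping groups, so pooling across classifications counts patients twice; newly enrolled patients without pre-policy data cannot supply the slope change

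*Combined protocol and SAP*

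**What the plan says.** Section 8.0, Subgroup analyses, applies the general models within subgroups. Groups (1) to (3) are defined by insurance history: insured for the whole period, insured only after the policy changes, and never insured. The next is "4) patients newly enrolled in the system after policy changes", and the last is open-ended: "5) other subgroups of interest according to gender, age (e.g., age 65 and older), race-ethnicity". The plan then turns to meta-analysis: "We will adopt this method to evaluate the average impact of policy changes across subgroups". The pool is to be built up step by step: "A forest plot will be generated to reveal how the addition of a subgroup to the meta-analysis may affect the average policy impact". The text does not say which groups enter one pool, whether they must be disjoint, or how correlation between their estimates is handled.

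On what is being pooled, section 8.0 reads policy impact from a contrast of trends: "the change in the trend/slope post-policy implementation may reveal the actual impact of the new policy controlling for baseline level and trend". In the segmented model the two relevant coefficients are described as "being the slopes (annual change in log odds) for the pre- and post-periods, respectively".

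Several policy dates appear. Section 2.1 gives 2012 for the CMS code, "which was followed by universal coverage by insurers for IBT for adults of all ages in 2013". Section 8.0 states "We set year 2014 as time origin for Utah when considering the policy impact of the ACA". Section 7.2 treats the Pennsylvania Medicaid expansion as the last change. None is tied to group (4).

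**The concern.** Standard meta-analysis weights each estimate by its inverse variance and treats the estimates as independent. That suits separate studies. Here the inputs would be subsets of one cohort. Every patient in groups (1) to (4) also has a gender, an age and a race-ethnicity, and group (4), defined by enrolment, can overlap the insurance groups. If groups from different classifications go into one pool, each further classification adds no patients but makes the interval narrower. A plot that adds groups one at a time would show this as growing precision.

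The second part concerns group (4). A patient first seen after the policy date may have no pre-policy year. A model fitted to such patients alone can give a post-policy trend but not a change of trend. Averaging that trend with slope changes from other groups would mix two different quantities.

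**Working it through.** The plan gives no figure for the pooled analysis, so there is nothing to reproduce first.

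**Inputs from the section 7.2 table (diabetes cohort).** Total 328,455; White 224,307; African-American 52,668; Other 51,480; female 161,761. The race rows sum to 328,455, so race is a complete classification. Gender is taken as complete, with the remaining 166,694 not female.

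**Minimum overlap.** White + female − total = 224,307 + 161,761 − 328,455 = 57,613 patients in both groups.

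**Pooling only the White and female groups.** Assume independent patients, equal variance and a common effect. With n₁ and n₂ the group sizes and m the overlap, the true SE divided by the nominal SE is √(1 + 2m/(n₁ + n₂)), where n₁ + n₂ = 386,068.

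| Overlap m | SE ratio | Coverage of nominal 95% interval |
|---|---|---|
| 57,613 (minimum) | 1.14 | 91.5% |
| 110,469 (gender and race independent) | 1.25 | 88.2% |
| 161,761 (maximum) | 1.36 | 85.2% |

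**Pooling K complete classifications, fixed effect.** The weighted mean within each classification reproduces the full-cohort mean, so the pooled estimate is that same mean. Its nominal variance is σ²/(KN), but its true variance is σ²/N. The interval therefore has 1/√K of the correct width, and coverage is 2Φ(1.96/√K) − 1. For gender plus race, K = 2: width 1/√2 = 71%, and coverage 2Φ(1.386) − 1 = 83%. For K = 1: 100% and 95%.

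**Random effects (DerSimonian-Laird), by simulation.** There were 4,000 replicates per case, with independent patients and additive category effects. The target was the patient-weighted average effect, and gender and race shares came from the table. The between-category SD is in units of one patient's SD and is an assumption.

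| Between-category SD | Gender plus race, n = 328,455 | Race alone, n = 328,455 |
|---|---|---|
| 0 | 85.7% | 96.4% |
| 0.005 | 92.3% | 98.2% |
| 0.01 | 97.4% | 99.2% |
| 0.02 | 99.4% | 99.8% |

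A separate rerun agreed to within about 1 percentage point.

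**Group (4).** The segmented model in section 8.0 has three columns: 1, min(t, 0) + 5, and max(t, 0). For t = −5 to 5 the rank is 3. If all observations have t ≥ 0, the second column equals 5 throughout, five times the first, and the rank is 2. Only β₀ + 5β₁ and β₂ can then be estimated; β₁, and so β₂ − β₁, cannot. One pre-policy year (t = −1 to 5) restores rank 3.

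**The case against.** The strongest reply is that the plan describes no error. It never says that all labels enter one pool or that overlapping estimates will be treated as independent. Its wording also fits pooling within each classification, and groups (1) to (3) are disjoint by definition. This stands: the double counting depends on how the text is carried out. But the plan offers one average over a list that overlaps, with groups added in turn, and followed literally that counts patients repeatedly.

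A reader might infer that the interval will be half its proper width, with 67% coverage. That is the K = 4 result (1/√4 = 50%). It needs four exhaustive classifications under a fixed-effect model, which the plan does not list: groups (1) to (3) leave out patients who lose or interrupt cover, (4) is a single group, and the age cut is only an example.

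The subgroup section starts from population heterogeneity, which would favour random effects, and under random effects the problem fades as heterogeneity grows. In the at-risk cohort of 2,062,499, using the diabetes cohort's gender and race shares, coverage for gender plus race is about 95% at an SD of only 0.0025 and 99% at 0.005. This too stands. Clustering works the other way, by lowering the effective sample size.

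The pooling model might be given in the sources cited for meta-analysis, numbered 16 and 17. The list in section 17.0 ends at 15, so this cannot be settled. Not naming the model, like not dating group (4), is missing detail and is not the defect argued here.

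On group (4), section 8.0 also describes a model using only post-policy data, and it allows shorter individual series. The post-policy model addresses the effect of the number of counselling visits, not the change from before to after the policy. Shorter series help a joint fit but not a fit to group (4) alone when no pre-policy year exists. Nor do the documents support reading every patient in group (4) as lacking a pre-period: claims data, or a later policy date, could supply one for some.

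**Conclusion.** The point holds in conditional form and is minor. If subgroups from different classifications are pooled by standard inverse-variance methods, patients are counted more than once and the interval for the average policy effect can be too narrow. Under a fixed-effect model with gender plus race, it has 71% of the correct width and 83% coverage. Under random effects, coverage at the diabetes cohort's size runs from about 86% with no heterogeneity to nominal or above at an SD of 0.01 or more. These figures assume independent patients of equal variance and illustrate the risk; they do not predict the result. Pooling within one exclusive classification is sound.

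For group (4) patients with no pre-policy observation, a separate fit of the segmented model cannot estimate the slope change. How many patients this affects depends on the policy date used and on the claims data available; the documents settle neither.

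A reader might infer that the trial's main policy estimate is compromised. It is not: it comes from the full-cohort individual-level model and does not use the subgroup pool. Estimates within the other subgroups are not affected either.

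**What to change.** Take the average policy effect from the full-cohort mixed model already planned in section 8.0. Test whether it varies by adding subgroup-by-slope interactions; that model already allows subject-level variables to act on the pre- and post-policy slopes. Use the forest plot for display only, or pool only within one mutually exclusive classification. Exclude from any slope-change estimate or pool those group (4) patients without pre-policy data, and report their post-policy level and trend descriptively. While editing, it would help to state the pooling model, if one is used, and the policy date that defines group (4).

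The cost is a few sentences in the statistical plan, with no new data. The downside is that there will be no single pooled figure across all subgroup labels, and the interval will be wider wherever double counting would have narrowed it.

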## Propensity scores matching

In the proposed modeling framework above, we adjust for the subject-level and cluster-level differences by including the exposure variables at different levels as covariates in the models. We also will consider a secondary analysis with a propensity scores matching approach to adjusting for these differences. A wide array of patient measures in the EHR, including demographics, insurance coverage, medical co-morbidities, health behaviors, and information on use of health care services, will be used to calculate the propensity scores. Propensity score-based stratification analysis will be performed to evaluate the overall impact of health policy using the modeling framework similar to that described above.

## Analyses of diabetes outcomes at population level

The primary analysis of our study focuses on the individual-level outcomes. The statistical models yield the estimate of average change at individual level post policy implementation. Given the information in the EHR data, we can also aggregate the diabetes outcomes at community level, clinic level, etc. For example, the proportion of patients with controlled diabetes can be obtained for each clinic and used as the outcome variable in the statistical modeling. The proposed mixed-effects modeling framework are still applicable in this case. The statistical analyses can be performed in a similar fashion to that for the individual-level outcomes.

For example, our proposed statistical analysis plan can be easily modified to compare the differences in weight loss and diabetes outcomes (including diabetes control, controlled blood pressure, use of a statin medication, receipt of an annual eye exam and annual urinary microalbumin test, and lower extremity amputations) between rural and urban areas. As stated in the proposal, although our main analysis is on individual-level outcomes, aggregated outcomes at the community- or county-level can also be extracted from the electronic health record (EHR) data. For example, the proportions of patients with controlled diabetes in each county at each year can be obtained and used as the outcome variable after arcsine-square root transformation in the statistical modeling. We can evaluate the rural/urban effects on the pattern of changes in diabetes outcomes over years by including county-level characteristics such as rural vs. urban in the mixed-effects models as fixed effects. The time origin in the analysis will be the beginning of the study period, rather than the time when insurance policy changes occurred. The counties sharing similar characteristics (e.g., access to the same health system) will be considered as a cluster and the clustering effect will be accounted for in the mixed-effects model analysis by including cluster-level random effects. Instead of using segmented regression models to evaluate the trend in diabetes outcomes before and after the policy change, we will consider linear or non-linear trends in the diabetes outcomes and allow rural and urban counties to have different patterns of changes in the models.

*Statistical Power.* Given the very large sample sizes that are anticipated for the research studies (more than 320,000 patients with diabetes and 2,000,000 patients at-risk for diabetes), there is tremendous statistical power to detect very small effect sizes for individual-level exposure variables. Therefore, the clinical investigators on this project will need to

examine each statistically significant result and determine whether it is clinically significant. Furthermore, such large sample sizes ensure the robust estimation results from the proposed multi-level statistical modeling which involves large number of regression coefficient and covariance parameters. The major benefit of the large sample size for each research study is that it provides sufficient statistical power for investigating effects of interest within subgroups that might be constructed according to age, race-ethnicity, cohort decompositions, etc.

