The proposed work leverages the novel infrastructure of the Patient-Centered Outcomes Research Institute-funded PaTH Clinical Data Research Network (CDRN), a partnership of four Mid-Atlantic academic health systems (Penn State Hershey Medical Center, University of Pittsburgh Medical Center, Temple Health System, and Johns Hopkins Health System) that have established governance to operate as an integrated research network. In 2015, the University of Utah and Geisinger Health System also joined PaTH, creating an electronic health record (EHR)-based data infrastructure across three states (Maryland, Pennsylvania, and Utah).

[figure not shown]
We have additionally added a focus on rural/urban differences in provision of obesity screening and counseling and the resultant impact on weight loss and diabetes incidence. Rural populations have a 17% higher prevalence of diabetes when compared to their urban counterparts. As a result, diabetes is the second highest priority for Rural Healthy People 2020. Additionally, rural populations have lower rates of guideline-concordant diabetes services, although this has been inadequately investigated. Studies report adults with diabetes living in rural communities are less likely to receive adequate diabetes-related care than non-rural residents, but are limited in study design (i.e., reliant on patient self-report or medical expenditure data). We propose leveraging the novel infrastructure of the Patient-Centered Outcomes Research Institute-funded PaTH CDRN to understand the rural and urban effects on diabetes and its complications. The integration of six large health institutions spanning a diversity of rural and urban populations has the unique opportunity to overcome limitations of prior studies by using health record data. In this way, our proposed study will address important gaps in our understanding of rural/urban differences in diabetes outcomes and guide future approaches to address and eliminate disparities.

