where  $\mathbf{x}_{mijk}$  is the vector of regressors for the fixed effects,  $\boldsymbol{\beta}_m$  is the corresponding vector of fixed-effects parameter coefficients,  $\mathbf{z}_{ij}$  is a vector of cluster-level regressors for the random effects for the  $j^{\text{th}}$  cluster of the  $i^{\text{th}}$  state,  $\boldsymbol{\gamma}_{1ij}$  is the cluster-level random-effect coefficients and is common to all  $m$ , and  $\boldsymbol{\gamma}_{2mijk}$  is the subject-level random-effect coefficients associated with the parameter  $\beta_m$  for the  $k^{\text{th}}$  subject within the  $j^{\text{th}}$  cluster. The random effects are assumed to follow a multivariate normal distribution with mean zero. Because the vector  $\mathbf{x}_{mijk}$  may include subject-level, cluster-level and state-level exposure variables, the fixed effects parameter vectors  $\boldsymbol{\beta}_1$  and  $\boldsymbol{\beta}_2$  represent the effects of different exposure variables on the annual changes in the pre- and post-periods. Thus, we may perform statistical tests to examine whether there are differences in trends between the pre- and post-periods overall and for each state, and whether the patterns of changes differ between the states.

Similarly for a count outcome  $Y_{ijkt}$  (e.g., number of clinical visits), we define the expected value  $\mu_{ijkt} = E(Y_{ijkt})$  and apply a Poisson regression model based on the natural log link function. The log expected number of clinical visits,  $\log(\mu_{ijkt})$ , can be modeled with the aforementioned segmented mixed-effects model. The use of an offset term in the models yields the estimates of the rate of clinical visits rather than the mean number of visits. The fixed-effect parameters,  $\beta_1$  and  $\beta_2$ , represent the effects of exposure variables on the annual changes in log of incidence rates for the pre- and post-periods, respectively. For a continuous outcome  $Y_{ijkt}$ , we will model the mean,  $\mu_{ijkt} = E(Y_{ijkt})$ , with the mixed-effects model and the parameters  $\beta_1$  and  $\beta_2$  indicate the effects of exposure variables on the annual changes in the outcomes for the pre- and post-periods, respectively. All final statistical models will be assessed with respect to the goodness-of-fit and the appropriateness of model assumptions. Statistical software SAS 9.4 and R environment will be used to implement the proposed analyses.

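### The secondary county-level rural/urban analysis does not say how the number of patients per county enters the model, although the arcsine-square-root transform leaves a variance that depends on it

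*Combined protocol and SAP*

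**What the plan says.** The relevant text is in section 8.0 of the combined protocol and SAP, under the analyses of diabetes outcomes at population level. The unit of analysis is the county-year: "the proportions of patients with controlled diabetes in each county at each year can be obtained". Each such value then enters the model in transformed form, being "used as the outcome variable after arcsine-square root transformation in the statistical modeling". The rural/urban effect is to be assessed "by including county-level characteristics such as rural vs. urban in the mixed-effects models as fixed effects". Counties with similar characteristics form clusters, and "the clustering effect will be accounted for in the mixed-effects model analysis by including cluster-level random effects".

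The same subsection sets the status of this work: "The primary analysis of our study focuses on the individual-level outcomes". The county analysis is introduced as an example of how the plan can be adapted.

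Two other statements in section 8.0 come close to the issue. The mixed-effects model is described as flexible enough to incorporate "heteroscedasticity of the variances and correlations". For count outcomes, "The use of an offset term in the models yields the estimates of the rate of clinical visits". Neither says how county size enters the model for county proportions.

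Section 2.1 makes the topic a declared interest: "We have additionally added a focus on rural/urban differences in provision of obesity screening and counseling".

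**The concern.** The arcsine-square-root transform removes the dependence of the sampling variance on the proportion p. It does not remove the dependence on the number of patients n. A county with 60 patients and one with 8,000 therefore give transformed values of very different reliability.

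If the model is fitted with one residual variance, both counties count the same. That wastes information. When county size differs between the groups being compared, it also misstates the standard error of the comparison. Rural counties are likely to be the smaller ones, so the unequal variance lines up with the exposure under test. At stake are the interval and test for the county-level rural/urban contrast, and the precision of the rural-by-time trend.

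**Working it through.** **Plan's own figure.** None exists: no standard error, power or sample size is given for the county analysis. The inputs are consistent. The five site counts in section 7.2 sum to the printed 328,455, and 48 + 19 = 67 Pennsylvania counties (section 2.1).

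**Inputs from the documents.** 48 rural and 19 urban Pennsylvania counties, with 27% of residents in rural counties (section 2.1). Diabetes patients at the three Pennsylvania sites tabulated in section 7.2: 25,219 + 150,589 + 40,536 = 216,344.

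**Assumptions.** Patients are spread by the 27%/73% residence split and evenly within each group. The between-county SD τ on the arcsine scale is 0 to 0.10. Alpha is two-sided 0.05. One of the six health systems has no column in the table, and eligibility limits will reduce counts, so I also show 5% of the counts.

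**Step 1, county size.**
- Rural: 216,344 × 0.27 / 48 ≈ 1,217 per county.
- Urban: 216,344 × 0.73 / 19 ≈ 8,312 per county, 6.8 times as many.
- Sampling SD, √(1/(4n)): 0.0143 rural and 0.0055 urban. The sampling variances differ 6.8-fold after the transform.

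**Step 2, standard error of the rural-urban difference.** Let s² = 1/(4n) + τ² in each group.
- Constant-variance SE: √[s²_pooled (1/48 + 1/19)], with s²_pooled = (47 s²_r + 18 s²_u)/65.
- True SE of the same estimate: √(s²_r/48 + s²_u/19).

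Example at full counts, τ = 0.02: s²_r = 0.000605, s²_u = 0.000430, s²_pooled = 0.000557. The constant-variance SE is 0.00640 and the true SE 0.00594, a ratio of 1.08. The false-positive rate is 2[1 − Φ(1.96 × 1.077)] ≈ 3.5%.

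| τ | Ratio at 1,217 / 8,312 | Ratio at 61 / 416 |
|---|---|---|
| 0 | 1.40 | 1.40 |
| 0.01 | 1.20 | 1.38 |
| 0.02 | 1.08 | 1.33 |
| 0.05 | 1.015 | 1.17 |
| 0.10 | 1.004 | 1.06 |

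**Step 3, direction.** The ratio exceeds 1 because the noisier group also has more counties. With the numbers reversed (19 small counties of 61 patients, 48 large of 416), the ratio is 0.71 at τ = 0 and 0.94 at τ = 0.10, so intervals would be too narrow. Section 2.1 also places the network in Maryland and Utah, whose county mix is not given.

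**Step 4, rural-by-time slope.** Simulation of 67 counties over 11 years with lognormal county sizes; county-year residual SD 0, 0.01 or 0.03; full or one-tenth counts; 2,000 replicates for each of six settings.
- Equal weights: model SE / true SE 1.08 to 1.45; false positives 0.7% to 2.9%.
- Weights 1/(1/(4n) + residual variance), with the residual variance taken as known: ratio 1.00 to 1.02; false positives 4.5% to 5.4%.
- Weighting cuts the true SE by about 1% (0.00084 to 0.00083; SD 0.03, full counts) to 48% (0.00140 to 0.00073; SD 0, one-tenth counts).
- Bias was negligible under both.

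**Step 5, check on the remedy.** A binomial model with no county-year term treats sampling as the only year-to-year noise. Let v = 1/(4n) and let σ be the county-year SD. The SE ratio for the slope is approximately √[(v_r/48 + v_u/19) / ((v_r + σ²)/48 + (v_u + σ²)/19)].
- At 1,217/8,312 and σ = 0.01 to 0.03 (assumed): 0.67 to 0.29, false positives about 19% to 58%.
- At 200/4,000 (assumed): 0.89 to 0.55, false positives about 8% to 28%.

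An extra-binomial component is therefore essential.

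**The case against.** The strongest reply is that this is silence, not a decision to ignore county size. Section 8.0 says mixed models can handle unequal variances and promises that final models will be checked for fit and assumptions. That is fair, and it rules out saying that the plan treats all counties alike by design. But describing what a model class can do does not commit this analysis to a variance function. The cluster random effects deal with correlation among similar counties, not with county size, and the offset is stated for count outcomes only.

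Second, the analysis is secondary and optional in tone. Table 1 in section 7.2 also lists rural versus urban among the individual-level and practice-level exposures, so the rural interest does not rest on county proportions alone. This stands and limits the importance of the point.

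Third, equal county weight is legitimate if the average county is the target. This also stands, but the plan does not name its target, and that target would not by itself justify a constant-variance standard error.

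A reader might infer that the rural/urban standard errors are simply wrong, or that a false rural/urban difference would appear. The documents support neither. At the full illustrative counts with τ of 0.05 or more, the error is 1.5% or less. In all settings with 48 rural and 19 urban counties it is conservative, and the simulated estimates were essentially unbiased.

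**Conclusion.** The concern holds as a gap in the specification of a secondary analysis. A concrete method is named, its variance depends on county size, and nothing in the plan brings county size into the model.

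With a constant residual variance and 48 rural versus 19 urban counties, the standard error of the rural-urban difference is about 1% to 40% too wide. The low end applies when between-county variation dominates, the high end when sampling noise dominates. For the simulated slope the excess was 8% to 45%. The error would reverse if the smaller-county group had fewer counties. All of this rests on assumed patients per county and assumed variances, because the documents give neither. A larger, fixed error should not be read into the plan, and the individual-level primary results are not touched.

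**What to change.** Specify one of two models for the county-year data:

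- **Preferred:** model the counts (number controlled out of number with diabetes) with a binomial logistic mixed model. Include county and cluster random effects, rural-by-time terms, and a county-year random effect or other overdispersion term. By Step 5, leaving out that last term could turn a conservative test into an anti-conservative one.
- **Alternative:** keep the transform, but set the residual variance to 1/(4n) plus an extra component estimated from the data.

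In either case, state whether the rural/urban contrast is meant for the average county or the average patient, and report the distribution of patients per county by rural status.

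The preferred model is consistent with the logistic mixed model already planned at patient level and gives odds ratios in place of arcsine-scale differences. The cost is a few lines of SAP text and a little more modelling work, with the same data and software.
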